#### Additional analyses

Multiple regression of both co-primary outcomes will be done to explore and adjust for the impact of potential baseline imbalances (SMDs exceeding 25%). If opportune, adjusted contrasts between analgesic techniques will be reported.

Also, exploratory analyses will be done on primary and secondary outcomes per treatment centre (strata).

#### Harms

As described in the study protocol under "Adverse events and harms monitoring", the risk classification of the OPtriAL is scored as having negligible risk for study subjects. Moreover, there will be no new medicinal interventions, and all doses of applied anaesthetics are already used in daily practice. All adverse events per participant will be recorded until the end of the study and followed until they have abated, or until a stable situation has been reached.

#### Statistical Software

Analysis will be performed using the Statistical Package for Social Sciences (IBM SPSS Statistics for Windows, Armonk, NY) version 29.

#### Declarations

#### Ethics approval and consent to participate

This study is performed in accordance with the declaration of Helsinki, 64th WMA General Assembly, Fortaleza, Brazil, October 2013 and in accordance with the Medical Research Involving Human Subjects Act (WMO, the Netherlands). The medical ethical committee of Utrecht University approved the study protocol (protocol number NL75375.041.20 version 02; METC-protocol number 20-787/D) and the amendment thereafter (version 03). In Belgium the medical ethical committee of the University Hospital in Antwerpen approved the study protocol (Project ID 20212021—0521—BUN B3002021000159). Prior to randomisation, written informed consent will be obtained from all participating patients.

#### Consent for publication

All participants have signed an informed consent which includes the consent for publication.

Data availability statement

The data that is originated from the OPtriAL study will be available through the FAIR principles (Findable, Accessible, Interoperable, and Reusable). The datasets and/or analysed data will be open access and available from the corresponding author on reasonable request. For a detailed data management plan, see our supplemental material Appendix C.

## Funding

The OPtriAL study to which this statistical analysis plan pertains, is a publicly funded research study.

The grant has been acknowledged by ZonMw, project number 10140021910007.

# 2C: Co-primary outcome QoR, ITT population

[figure not shown]
[figure not shown]

Figure 3:

3a. Linear mixed model for pain scores in rest and mobilizing from baseline, POD 0-3 and follow-up for each analgesic technique (lines represent hypothetical data)

3b. Linear mixed model for quality of recovery from baseline, POD 0-3 and follow-up for each analgesic technique (lines represent hypothetical data)

[figure not shown]
[figure not shown]
[figure not shown]

Figure 4: Generalized estimating equations for Patient Satisfaction and Mobility (including hypothetical data)

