Non-inferiority for pain is obtained only if the upper limit of the 98.65% one-sided confidence interval (CI) of the differences of mean proportion of NRS  $\geq$ 4 between the PVB versus TEA and ICNB versus TEA remains below the predetermined absolute margin of 17.5% in the intention-to-treat (ITT) analysis as well as in the per-protocol (PP) analysis. This non-inferiority margin is based on data from a previous pilot study, in which the proportion of pain scores  $\geq$  4 in a group of patients receiving TEA was 17.57% (SD 19.57) and in patients receiving continuous locoregional analgesia 21.21% (SD 23.33). Since the baseline of 17.57% of moments of pain in the control group is low, we accept an absolute margin of 17.5% from a clinical point of view. This margin of non-inferiority, accepting more moments of pain in the intervention techniques as compared to the control group, is justifiable in combination with superiority regarding QoR. Superiority regarding QoR is defined as a significantly higher mean score during POD 1 and POD 2 (p < 0.027) in the ITT analysis. Taking the mean QoR score during POD 1 and POD 2 is a simplifying improvement of the original superiority definition in the published study protocol (1) without affecting the sample size calculation.

Secondary outcomes are: 1) pain scores during rest and mobilization at the recovery room, in the evening of the day of operation, and in the morning, afternoon and evening on POD 1 until POD 3, and at 2-3 weeks follow-up; 2) proportion of NRS scores ≥4 during mobilization during POD 0 until 2; 3) QoR-15 at POD 0, POD 3 and 2-3 weeks follow-up; 4) cumulative use of opioids and analgesics at POD 0 until 3 and the plain use of opioids at 2-3 weeks follow-up; 5) postoperative complications until POD 30; 6) hospitalisation; 7) patient satisfaction at POD 0 until 3; 8) time to removal of the chest tube; 9) time of an indwelling urinary catheter; 10) degree of mobility at POD 0 until 3 and 11) cost-effectiveness analysis (separate analysis).

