#### Patient satisfaction

Patient satisfaction is scored from POD 0 until 3 in a patient diary using a 5-point Likert scale (extremely dissatisfied, dissatisfied, neutral, satisfied, extremely satisfied). This categorical outcome will be analysed as with Mantel-Haenszel chi-squared test or Fisher's exact test (Figure 4a).

Presence of chest tube

The presence of the postoperative chest tube will be registered in whole nights during hospital admission as outcome measure with differences between the groups analysed with T-test or Mann-Whitney U-test (Table 3).

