#### Degree of mobility

Degree of mobility was recorded in the patient diary using a 4-point Likert scale (only in bed, from bed to chair, from bed to the toilet, outside of the patient room). This categorical outcome will be analysed with Mantel-Haenszel chi-squared test or Fisher's exact test (Figure 4b).

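### Satisfaction and mobility over POD 0–3: the text and Appendix A plan Mantel-Haenszel or Fisher tests, Figure 4 says GEE, and the unit of analysis is not defined

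*SAP*

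**What the plan says.** On satisfaction, the SAP section *Patient satisfaction* states: "Patient satisfaction is scored from POD 0 until 3 in a patient diary using a 5-point Likert scale". The test sentence reads "This categorical outcome will be analysed as with Mantel-Haenszel chi-squared test or Fisher's exact test (Figure 4a", so it points to Figure 4a.

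On mobility, the section *Degree of mobility* states: "Degree of mobility was recorded in the patient diary using a 4-point Likert scale". It gives no days; these are in *Summary of the study protocol*, which lists "degree of mobility at POD 0 until 3". The test sentence is "This categorical outcome will be analysed with Mantel-Haenszel chi-squared test or Fisher's exact test (Figure 4b", pointing to Figure 4b.

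Appendix A has one row for each outcome and names the same two tests. It gives neither a day nor a per-patient summary.

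The caption of Figure 4, which both test sentences cite, is "Generalized estimating equations for Patient Satisfaction and Mobility (including hypothetical data". No link function, working correlation, time term or contrast is given for a GEE anywhere in the SAP.

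Secondary outcomes are tested at 0.027 per comparison (*Secondary outcomes*), with no further multiplicity correction (*Analysis principles and general considerations*).

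**The concern.** Each patient can contribute up to four ratings per outcome if the diary is daily. Ratings from one patient are likely to be correlated. The SAP accepts this for pain, where *Pain scores during rest and mobilisation* rejects independence of repeated scores and uses a linear mixed model; QoR-15 over time is also given a mixed model. For satisfaction and mobility the text names tests for independent observations, while the figure names a method built for correlated ones.

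Two analysts following the document could therefore produce different p-values, and some routes give p-values that are too small. Mobility matters to the argument: the abstract lists it among the outcomes tested for superiority, and faster mobilisation is part of the rationale for moving away from TEA. The trial is unblinded, so the method and the unit of analysis should be fixed beforehand.

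**Working it through.** **1. The places side by side**

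| Place in the SAP | Method | Unit over POD 0–3 |
|---|---|---|
| *Patient satisfaction* | Mantel-Haenszel or Fisher, citing Figure 4a | not stated |
| *Degree of mobility* | Mantel-Haenszel or Fisher, citing Figure 4b | not stated |
| Appendix A | Mantel-Haenszel or Fisher | not stated |
| Figure 4 caption | GEE | not stated |

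For the other two outcomes followed over time, pain scores and QoR-15, the text, Figure 3 and Appendix A all name the linear mixed model. The mismatch is specific to these two outcomes.

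**2. The nominal level**

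Two experimental arms share one control, so the two test statistics have correlation 0.5. Taking a two-sided family-wise level of 5%, the Dunnett-type critical value is 2.212. The per-comparison level is 2 × (1 − Φ(2.212)) = 0.02696, which rounds to the SAP's 0.027.

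**3. Inputs for the error-rate check**

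- Patients per arm: 150 × (1 − 0.126) = 131.1, taken as 131 (*Summary of the study protocol*).
- Days: 4 (POD 0 to 3), complete diaries assumed.
- Scales: 5-point (satisfaction) and 4-point (mobility).
- Within-patient correlation: not in the SAP. Assumed equal between all days on a latent normal scale, 0.3 to 0.5 as the main range, with 0 and 0.7 as checks.
- Category distribution: not in the SAP. Assumed from fixed cut-points on the latent scale, with the mean rising by 0.2 a day.

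**4. Simulated type I error, no treatment effect, nominal 0.027**

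There were 5,000 runs per setting. The Monte Carlo standard error is about 0.002 near 0.027 and 0.005 near 0.14. Each cell gives 5-point / 4-point.

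| Reading of the plan | Correlation 0.3 | Correlation 0.5 |
|---|---|---|
| Days pooled, Pearson chi-squared | 0.058 / 0.064 | 0.100 / 0.116 |
| Days pooled, Mantel-Haenszel trend | 0.090 / 0.087 | 0.133 / 0.135 |
| Mantel-Haenszel stratified by day | 0.097 / 0.093 | 0.140 / 0.143 |
| One test on one day | 0.028 / 0.032 | 0.024 / 0.031 |
| Any of four daily tests | 0.106 / 0.101 | 0.086 / 0.106 |
| Patient-level comparison of mean scores | 0.032 / 0.027 | 0.028 / 0.032 |

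At correlation 0 (5-point scale only), the pooled and day-stratified tests give 0.022 to 0.027. At 0.7 they give 0.164 to 0.191. The inflation therefore comes from the correlation alone.

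The last row is equivalent to an identity-link GEE on the score with an independence working correlation and robust variance. It was not run as a cumulative-logit GEE; it shows that clustering on the patient restores the level.

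**5. Cross-checks**

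- *Pooling.* The design effect is 1 + 3ρ, or 1.9 at ρ = 0.3 and 2.5 at ρ = 0.5. With critical value 2.2115 for 0.027, the true error is 2 × (1 − Φ(2.2115/√1.9)) = 0.109 and 2 × (1 − Φ(2.2115/√2.5)) = 0.162. These exceed the simulated values partly because ρ here is the correlation of the scores themselves, not of the latent scale. Direction and order of magnitude agree.
- *Four daily tests.* If independent, 1 − (1 − 0.027)⁴ = 0.104. Over all correlations simulated (0 to 0.7) the range is 0.079 to 0.106.

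**The case against.** The strongest reply is that the plan has settled the method. *Analysis principles and general considerations* names Appendix A as the overview of planned tests, Appendix A agrees with both outcome sections, and *Statistical principles* describes the figures as hypothetical illustrations. On that view the caption is a slip. This carries weight for the choice of method, so it would be too strong to say that the choice is simply left until the data are seen. It does not answer the second gap: none of those places says which day, or which per-patient value, is tested.

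A reader might infer that the Mantel-Haenszel or Fisher test necessarily gives p-values that are too small. The document does not support that. It never says that the days are pooled or stratified by day, and a test on one day or on one value per patient uses independent data and holds its level.

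A reader might also count the false-positive chance over four daily tests as a fault of these tests. Each daily test is about nominal, and the absence of correction is a declared policy for all secondary outcomes.

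Fisher's test is only a fallback for zero cells when merging categories is unsuitable. Ignoring the category order costs power; it does not inflate error.

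Finally, naming a day or a per-patient summary and correcting the caption would also remove the contradiction. That is true, though a single day would discard most of the diary data.

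**Conclusion.** The contradiction between the text with Appendix A and the cited figure is certain, and so is the undefined unit of analysis. The inflation is conditional. If days are pooled or stratified by day as though independent, the true error is about 0.06 to 0.14 against 0.027, or two to five times nominal. This rests on assumed latent correlations of 0.3 to 0.5, assumed category distributions, 131 patients per arm and complete diaries. With one day or one value per patient there is no inflation. With four daily tests the chance of at least one false positive is about 8 to 11% per outcome and comparison, under the SAP's declared policy.

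It would be wrong to infer that the trial's main conclusions are at risk. These are two secondary outcomes, and non-inferiority and superiority rest on pain and QoR-15 alone. The point should be corrected before analysis.

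**What to change.** Make the Figure 4 method the planned test, and replace the Mantel-Haenszel and Fisher entries in *Patient satisfaction*, *Degree of mobility* and the two Appendix A rows. Specify:

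- a cumulative-logit GEE with patient as cluster, a stated working correlation and robust standard errors;
- day, centre and treatment in the model, with a treatment effect common to POD 0–3 as the single contrast for PVB versus TEA and for ICNB versus TEA, each at 0.027;
- treatment-by-day terms and daily distributions as descriptive only, because a model with that interaction has no single overall contrast unless day weights are stated;
- the days on which mobility is scored, in its own section.

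Add a sensitivity analysis for missing diary scores. Standard GEE assumes scores are missing completely at random. *Patient replacement and missing data* makes provision for stays of two days or less, so later scores may be absent for the patients who recover fastest. Inverse probability weighting or an ordinal mixed model would serve.

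The cost is a few lines of SAP text and some extra analysis work, with no change to data collection. Sparse categories may have to be merged, by a rule written down beforehand. The team should confirm that the named software fits the model.

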## 4a: Patient Satisfaction

## 4b: Patient mobility

Patient characteristics	Thoracic Epidural Analgesia (N=)	Paravertebral block (N=)	Intercostal Nerve Block (N=)
Age — yr			
Body-mass index			
Female sex — no. (%)			
Smoking status — no. (%)			
Smoker			
Non-smoker			
Ex-smoker			
WHO performance state — no. (%)			
WHO 0-1			
WHO 2-3			
WHO 4			
Comorbidities — no. (%)			
COPD (GOLD I, II, III and IV)			
Previous thoracic surgery/RXT			
Pain syndromes			
Psychiatric conditions			
Operation indication — no. (%)			
Primary lung cancer			
Metastasis			
Diagnostic			
Benign lesion			
Pathological TNM stage — no. (%)			
T1			
T2			
Т3			
T4			
NO			
N1			
N2			
N3			
Baseline surgical characteristics			
Operation technique — no. (%)			
Uniportal VATS			
Multiport VATS			
Type of resection — no. (%)			
Segmentectomy(ies)			
Lobectomy			
Bi-lobectomy			
Pneumonectomy			
Operating time — min			
One chest tube — no. (%)			
Baseline anaesthesiology characteristics			
Pre-operative			
Analgesics — no. (%)			
Paracetamol			
Paracetamol NSAIDs			

Table 1: Baseline patient, surgical and pain characteristics

Benzodiazepine — no. (%)
Peri-operative
Induction analgesia — no. (%)
Propofol
Benzodiazepine
Opioids
Muscle relaxant
Local anaesthetics
Sustained analgesia — no. (%)
Propofol
Benzodiazepine
Opioids
Muscle relaxant
Local anaesthetics
Dexamethasone — mg
Antiemetic — no. (%)
Vasopressives — no. (%)
Plus-minus values are means ±SD. WHO denotes World Health Organisation, TNM denotes Tumor, Nodes and Metastasis, VATS denotes

video-assisted thoracoscopic surgery, NSAIDs denotes non-steroidal anti-inflammatory drugs, NRS denotes numerical rating scale. Body-mass index is the weight in kilograms divided by the square of the height in meters.

TEA: thoracic epidural analgesia; PVB: paravertebral block; ICNB: single-shot intercostal block; BMI: body mass index; No.: number; COPD: chronic obstructive pulmonary disease; GOLD: Global Initiative for Chronic Obstructive Lung Disease; TNM: tumour nodes metastasis; VATS: video-assisted thoracoscopic surgery; NRS: numerical rating scale

Table 2: Performance of analgesic techniques

2A: Details regarding the execution of the thoracic epidural analgesia

```
Procedure TEA
Number of times executed
Preoperative placement — no. (%)
Placement by the anaesthesiologist - no. (%)
Test dose epidural given - no. (%)
         Volume (mL)
Local analgesics given
         Ropivacaine — no. (%)
                 Concentration ropivacaine (mg/mL)
         Bupivacaine — no. (%)
                Concentration bupivacaine (mg/mL)
         Levobupivacaine — no. (%)
            Concentration levobupivacaine (mg/mL)
Opioids given — no. (%)
         Sufentanyl
                   Concentration sufentanyl (ug/ml)
Perioperative infusion rate — (ml/hour)
Postoperative infusion rate — (ml/hour)
Days in situ after operation — (days)
```

2B: Details regarding the execution of the paravertebral block

#### **Procedure PVB**

Number of times executed Executed at the beginning of the operation — no. (%) Executed by the lung surgeon — no. (%) Bolus ropivacaine 7.5 mg/mL — no. (%) Volume (mL) Days in situ after operation (days)

2C: Details regarding the execution of the single-shot intercostal nerve block

#### **Procedure ICNB**

```
Number of time executed

Executed at the end of the operation — no. (%)

Executed by the lung surgeon — no. (%)

Local analgesic given

Ropivacaine — no. (%)

Concentration ropivacaine (mg/mL)

Bupivacaine — no. (%)

Concentration bupivacaine (mg/mL)

Levobupivacaine — no. (%)

Concentration levobupivacaine (mg/mL)

Total volume given (mL)

From thoracic level 2 to 10 — no. (%)
```

Table 3: Secondary outcome measures

Outcome	Thoracic Epidural Analgesia (N=)	Paravertebral block (N=)	p-value 	Intercostal Nerve Block (N=)	p-value 
Percentage of NRS≥4 during mobilizing POD 0-3	()	(12)		(11)	
Percentage of NRS≥4 at rest POD 0-3					
Analgesics and opioids at POD 0					
Paracetamol (mg)					
NSAID's (mg)					
Opioids (MME)					
Optional: opioids when MME not applicable					
Analgesics and opioids at POD 1					
Paracetamol (mg)					
NSAID's (mg)					
Opioids (MME)					
Optional: opioids when MME not					
applicable					
Analgesics and opioids at POD 2					
Paracetamol (mg)					
NSAID's (mg)					
Opioids (MME)					
Optional: when MME not applicable					
Analgesics and opioids at POD 3					
Paracetamol (mg)					
NSAID's (mg)					
Opioids (MME)					
Optional: when MME not applicable					
Postoperative complications — no. (%)					
CD 1 and 2					
CD 3 and 4					
CD 5 (mortality)					
Hospitalisation (days)					
Time to removal of chest tube (days)					
Presence of urinary catheter (days)					
Plus-minus values are means ±SD. NRS denotes numerical		denotes postoperative of		tes milligrams of	

morfine equivalent; NSAIDs denotes non-steroidal anti-inflammatory drugs.CD denotes Clavien Dindo; p-value for the comparison between TEA and IVB; p-value for the comparison between TEA and ICNB

# Table S1: Standardized mean differences for baseline characteristics of the ITT

# population

Patient characteristics	Thoracic Epidural Analgesia (N=)	Paravertebral block (N=)	SMD 	Intercostal Nerve Block (N=)	SMD 
Age — yr	( )	( )		( )	
Body-mass index					
Female sex — no. (%)					
Smoking status — no. (%)					
Smoker					
Non-smoker					
Ex-smoker					
WHO performance state — no. (%)					
WHO 0-1					
WHO 2-3					
WHO 4					
Comorbidities — no. (%)					
COPD (GOLD I, II, III and IV)					
Previous thoracic surgery/RXT					
Pain syndromes					
Psychiatric conditions					
Operation indication — no. (%)					
Primary lung cancer					
Metastasis					
Diagnostic					
Benign lesion					
Pathological TNM stage — no. (%)					
T1					
T2					
Т3					
Τ4					
NO					
N1					
N2					
N3					

# **Baseline surgical characteristics**

Operation technique — no. (%) **Uniportal VATS** Multiport VATS Type of resection - no. (%) Segmentectomy(ies) Lobectomy **Bi-lobectomy** Pneumonectomy Operating time — min One chest tube — no. (%) **Baseline anaesthesiology** characteristics **Pre-operative** Analgesics — no. (%) Paracetamol **NSAIDs** Opioids Benzodiazepine — no. (%) **Peri-operative** Induction analgesia — no. (%) Propofol Benzodiazepine Opioids Muscle relaxant Local anaesthetics Sustained analgesia — no. (%) Propofol Benzodiazepine Opioids Muscle relaxant Local anaesthetics Dexamethasone — mg Antiemetic - no. (%) Vasopressives — no. (%)

SMD: TEA versus PVB; SMD: TEA versus ICNB. Plus–minus values are means ±SD. WHO denotes World Health Organisation, TNM denotes Tumor, Nodes and Metastasis, VATS denotes video-assisted thoracoscopic surgery, NSAIDs denotes non-steroidal anti-inflammatory drugs, NRS denotes numerical rating scale.

Body-mass index is the weight in kilograms divided by the square of the height in meters.

TEA: thoracic epidural analgesia; PVB: paravertebral block; ICNB: single-shot intercostal block; BMI: body mass index; No.: number; COPD: chronic obstructive pulmonary disease; GOLD: Global Initiative for Chronic Obstructive Lung Disease; TNM: tumour nodes metastasis; VATS: video-assisted thoracoscopic surgery; NRS: numerical rating scale

# Appendix A. Overview statistical test per outcome

Outcome	Planned statistical test to compare
	randomization groups (each intervention versus
	control)
Baseline characteristics	None*
Primary outcome	
% NRS ≥ 4 POD 0-2 (at rest)	Non-inferiority, upper limit 98.6% CI <17.5%
Mean QoR-15 POD 1-2	Unpaired t-test or Mann-Whitney U-test
Secondary outcomes	
% NRS $\geq$ 4 POD 0-2 (mobilization)	Unpaired t-test or Mann-Whitney U-test
% NRS $\geq$ 4 baseline, POD 0-3 and follow-up (at rest)	Linear mixed model
% NRS $\geq$ 4 baseline, POD 0-3 and follow-up	Linear mixed model
(mobilization)	
QoR-15 at baseline, POD 0-3 and follow-up	Linear mixed model
Cumulative use of analgesics POD 0-3	Unpaired t-test or Mann-Whitney U-test
Cumulative use of opioids POD 0-3	Unpaired t-test or Mann-Whitney U-test
Cumulative use of analgesics (including opioids) at follow-up	Unpaired t-test or Mann-Whitney U-test
Postoperative complications	Mantel-Haenszel chi-squared test or Fisher's
	exact test
Length of hospitalization	Mann-Whitney U-test
Patient satisfaction	Mantel-Haenszel chi-squared test or Fisher's
	exact test
Presence of chest drain	Unpaired t-test or Mann-Whitney U-test
Presence of urinary catheter	Unpaired t-test or Mann-Whitney U-test
Degree of mobility	Mantel-Haenszel chi-squared test or Fisher's exact test

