#### Summary of the study protocol

The OPtriAL (Optimal postoperative Pain management After thoracoscopic Lung resection) is a threearm multicentre pragmatic randomized controlled trial comparing TEA, continuous PVB and single-

shot ICNB in adult patients undergoing thoracoscopic anatomical lung resection. The study comprises two co-primary outcomes with different designs: a non-inferiority design for the outcome 'pain' and a concomitant superiority design for the outcome 'quality of recovery'.

Adult patients (>18 years) referred for thoracoscopic anatomic lung resection (segmentectomy, (bi)lobectomy and pneumonectomy for either benign or malignant disease) are eligible for the trial. We exclude patients with a contraindication for one of the analgesic techniques, chronic use of opioids, a high probability of conversion to thoracotomy or in case of insufficient Dutch proficiency. Written informed consent is obtained from each participating patient before randomisation. Patients are randomized in a 1:1:1 ratio for one of the three analgesic techniques by a computerized database (Research Manager) with an unchangeable computer-generated number. Randomization is done in random block sizes of 6, 9 and 12. As anaesthesia and surgical protocols may slightly differ between hospitals, randomization is stratified by treatment centre. Blinding is unfeasible due to clear visible differences of the analgesic techniques and would potentially compromise the safety of the patient (analgesic catheter, indwelling urinary catheter, mobility with or without prerequisites).

The first co-primary outcome relates to pain and the second to QoR. Pain is measured with the numerical rating scale (NRS 0-10; 0=no pain, 10=worst imaginable pain). A NRS score <4 indicates acceptable pain and ≥4 indicates unacceptable pain as it implies the clinical need for additional analgesia. Therefore, our primary outcome 'pain' for non-inferiority is expressed as the proportion of postoperative NRS scores in rest ≥4, defined as the number of NRS ≥4 measurements divided by the total number of NRS measurements obtained from postoperative day (POD) 0 until POD 2. Each patient has a maximum of 8 measurements: at the recovery room, the evening of the day of the operation, and in the morning, afternoon and evening of POD 1 and 2. Superiority of the second coprimary outcome 'QoR' is measured with the QoR-15 questionnaire (lowest score of 0 and highest score of 150) at POD 1 and POD 2.

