#### Protocol violation, adherence and deviation

Protocol violation is defined as non-adherence to the eligibility criteria, randomization process and study procedures, dictating that all patients should participate voluntarily and undergo an anatomical lung resection by VATS and one of the analgesic techniques (TEA, PVB or ICNB).

Protocol adherence defines that control patients should proceed to PVB catheter placement in case TEA catheter placement was unsuccessful; in case PVB too was unsuccessful, then ICNB should be done. Participants receiving TEA or PVB should have a provisional stop of the continuous analgesia at POD 2 and patients receiving TEA should have opioids administered through the epidural continuous mixture. Accidental luxation of the TEA or PVB catheter after surgery will not be seen as nonadherence.

Although the use of ERATS guidelines for enhanced postoperative recovery were advised by the protocol, it is expected that the level of implementation of each aspect of ERATS differs per hospital, for example the strict use of dexamethasone and 5-HT3 receptor antagonists. In addition, the availability of specific local anaesthetics (e.g. bupivacaine or ropivacaine) may vary and induce small between-hospital differences. To ensure equal distribution of small differences in ERATS aspects, we used treatment centre as stratification factor. Incomplete primary or secondary endpoints are considered a protocol deviation and are handled as missing data.

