#### Pain scores during rest and mobilisation

Pain scores in rest and during mobilisation will be registered at: baseline (pre-operatively); at the recovery room and in the evening of POD 0; in the morning, afternoon, and evening of POD 1-3 and at the follow-up appointment, generating 13 moments in which the pain scores are prospectively measured. Since pain scores are repeated measurements from the same patient, they are likely to be correlated and we cannot assume independency. As we expect the effect of analgesia is patient-specific and will therefore vary substantially from patient to patient, a linear mixed model will be used (Figure 3a). This analysis will lead to a more precise estimate of the trend in pain scores and how this outcome changes over time per analgesic technique. The model will include random intercepts, and baseline scores, time of the measurement and treatment group as fixed effects. The

linear mixed model will accommodate unbalanced data patterns by assuming missing data at random and use all available observations and patients in the analysis (10). We will apply the covariance matrix that fits best according to Akaike's Information Criterion (AIC) (11).

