DANS (Data Archiving and Networked Services)

6.5 After the project, I will use the recommended minimum retention period of at least 10 years for my data.

• Yes (specify the number of years)

15 years according to the Dutch Act on Medical Research Involving Human Subjects (WMO) and Good Clinical Practice (GCP) guidelines.

6.6 The costs for data management during the project and data preparation for archiving are covered in the project budget.

• Yes (explain)

The costs are included in the budget submitted to ZonMw. The costs for local data management in a multicenter trial with a minimum of 10 participating centers, taking into account the protocol and Case Report Form (CRF), are estimated to be €128,458.05. Central data management, creation of a codebook, and an SPSS data file are tasks performed by the research doctor.

6.7 The costs of (data preparation for) archiving are covered.

• Yes (explain)

The costs for storing questionnaire data are covered by IKNL. The costs for storing clinical data in Research Manager are included in the license held by Máxima Medisch Centrum. The costs for storing local documents and data processing software are covered by Máxima Medisch Centrum.

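### Randomisation is stratified by centre, but the tests for stay, drain, catheter and drug use, and the pain mixed model as listed, leave centre out; if centre predicts these outcomes, some power is lost.

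*SAP*

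**What the plan says.** **Design.** Under Summary of the study protocol, "randomization is stratified by treatment centre", for the reason "As anaesthesia and surgical protocols may slightly differ between hospitals". Allocation is 1:1:1, and "Randomization is done in random block sizes of 6, 9 and 12". Under Protocol violation, adherence and deviation the SAP adds that "it is expected that the level of implementation of each aspect of ERATS differs per hospital", and gives this as the purpose of stratifying. The same section says that the choice of local anaesthetic may "induce small between-hospital differences".

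**Secondary tests.** Appendix A lists "Length of hospitalization Mann-Whitney U-test". It gives a t-test or Mann-Whitney test for chest drain, urinary catheter, analgesics and opioids. The text sections on these outcomes agree with it, and none mentions centre.

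**Mixed models.** For pain scores: "The model will include random intercepts, and baseline scores, time of the measurement and treatment group as fixed effects". The QoR-15 section names a linear mixed model without listing its terms.

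**Categorical outcomes.** Complications, satisfaction and mobility get a Mantel-Haenszel chi-squared test or Fisher's exact test, with no stratum named. The caption of Figure 4 gives generalized estimating equations for satisfaction and mobility instead.

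**Where centre does appear.** Additional analyses plans exploratory analyses within each centre. The regression adjustment in that section covers only the co-primary outcomes, for baseline factors with a standardised mean difference above 25%.

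**The concern.** Blocking within centre makes the arms nearly balanced on centre, so differences between hospitals largely cancel from the comparison of arms. A test that ignores the strata still counts the spread between hospitals as random error. Its standard error is then larger than the true one. Under the null hypothesis it rejects less often than 0.027 allows, and under a real effect it has less power than a stratified test on the same data.

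These tests carry conclusions. The abstract says that stay, complications and mobility will be tested for superiority, and the Secondary outcomes section tests all secondary outcomes at p<0.027. The Background names mobilisation, morbidity and hospital stay as possible benefits of the alternative techniques. The SAP gives no reason for leaving the stratification factor out, and analyses within single centres do not supply a centre-adjusted comparison of arms.

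**Working it through.** **Inputs from the SAP.** 150 patients per arm, 12.6% drop-out, level 0.027 (taken as two-sided, as for QoR), blocks of 6, 9 and 12, and, from a budget item in Appendix C, a "multicenter trial with a minimum of 10 participating centers". Analysed patients per arm: 150 × (1 − 0.126) = 131.

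**The plan's own figure.** The SAP states no power for any secondary outcome. Its 99% power for non-inferiority on pain serves only to check the base of 131 per arm:
- SD = √((19.57² + 23.33²)/2) = 21.53
- SE = 21.53 × √(2/131) = 2.66
- true difference = 21.21 − 17.57 = 3.64
- power = Φ((17.5 − 3.64)/2.66 − 2.21) = Φ(3.00) = 99.9%

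This is consistent with the stated 99%.

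**Assumption.** Let ρ be the share of outcome variance that lies between centres. The SAP gives no value, so a range is used.

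**Formula.** With n per arm and total variance σ², the unstratified test uses 2σ²/n for the variance of the difference. Under centre-stratified blocks the true variance is about (1 − ρ) × 2σ²/n. With z = 2.21 (two-sided 0.027):
- actual type I error = 2 × (1 − Φ(z/√(1 − ρ)))
- power of the unstratified test = Φ(z + z_power − z/√(1 − ρ)), where z_power is the normal quantile of the adjusted test's power (0.84 for 80%)

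Example, ρ = 0.20: z/√0.80 = 2.47. Type I error is 0.0134, and power is Φ(2.21 + 0.84 − 2.47) = Φ(0.58) = 71.9%.

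| ρ | Type I error | Power if adjusted test has 80% | Power if adjusted test has 90% |
|---|---|---|---|
| 0.02 | 0.0255 | 79.4% | 89.6% |
| 0.05 | 0.0233 | 78.4% | 89.0% |
| 0.10 | 0.0197 | 76.5% | 87.7% |
| 0.20 | 0.0134 | 71.9% | 84.6% |

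**Simulation of skewed stay in whole nights: power of Mann-Whitney versus van Elteren.**
- A: 10 centres, about 131 per arm, 4,000 trials per setting, shift of 0.40 total SD on the log scale.
- B: 450 randomised, 12.6% excluded at random afterwards, 10 equal centres, shift of 0.36 SD, 2,500 trials per setting.
- C: as B, with 14 centres of assumed sizes 3 to 110.

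| ρ | A | B | C |
|---|---|---|---|
| 0 | 80.8 vs 79.8% | 72.0 vs 70.9% | 72.4 vs 71.0% |
| 0.02 | 82.7 vs 82.6% | 72.6 vs 71.6% | 70.4 vs 69.2% |
| 0.05 | 83.9 vs 83.8% | 70.4 vs 70.6% | 69.7 vs 69.9% |
| 0.10 | 82.5 vs 84.2% | 68.0 vs 70.5% | 68.9 vs 70.6% |
| 0.20 | 84.8 vs 88.9% | 63.8 vs 71.7% | 63.6 vs 70.1% |

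In A at ρ = 0.20, type I error was 0.018 for Mann-Whitney and 0.027 for van Elteren. The Mann-Whitney p-value was the larger of the two in 39% of trials at ρ = 0, 55% at 0.05, 67% at 0.10 and 83% at 0.20. So the excess holds on average, not in every trial.

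**Binary outcome** (30% rate, odds ratio 0.45), single-table versus centre-stratified Mantel-Haenszel: power 67.3 vs 67.7% at a latent share of 0.03, 64.9 vs 67.1% at 0.10 and 59.4 vs 64.5% at 0.20.

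**Reading.** Up to ρ = 0.05 the loss is at most 1.6 points by formula (80% − 78.4%), and the simulated rank tests show no material loss. At 0.10 it is about 2 to 3 points (1.7 to 2.5 simulated, 3.5 by formula at 80%). At 0.20 it runs from 4.1 points (A) to 8.1 (formula at 80%).

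**The case against.** The strongest reply is that the planned tests are valid and that the loss may be negligible. The SAP describes the differences in protocols as slight and those in ERATS aspects and local anaesthetics as small. At a centre share of 2% or less the plain Mann-Whitney test is level with the stratified test or up to about 1 point better, and at 5% the two tie. No secondary outcome has a stated power to fall short of, and ten centres is only a minimum from a budget line. All of this stands, and it makes the size conditional.

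It does not justify the choice. The same SAP expects ERATS implementation to differ per hospital and stratifies for that reason. It never argues that centre may be dropped from the analysis.

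A reader might infer more than the document supports:

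- *That p-values are too large and power is lost, as a fact.* This depends on centre being prognostic, and the SAP gives no figure for that.
- *That the complications test ignores centre.* A Mantel-Haenszel test can be run within strata or on one table. The Fisher alternative and the cited papers on two-by-two tables make one table the likelier reading, but the stratum is unspecified, not shown to be absent.
- *That the satisfaction and mobility tests ignore centre.* The SAP names two different methods for them, so the method is not settled.
- *That these are the outcomes most dependent on local practice.* The SAP does not say so.
- *That the mixed model excludes centre.* Centre is not among its listed fixed effects. The level of the random intercepts is not named, although the surrounding text speaks only of repeated measurements within patients.

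**Conclusion.** The point holds as one of efficiency. Stay, drain, catheter and drug use are to be compared without the randomisation strata, and the pain mixed model lists no centre effect. The exploratory analyses per centre do not repair this. If centre predicts the outcome, the tests are conservative on average.

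The cost is about nil (at most 1 to 2 power points) for centre shares up to 5%, about 2 to 3 points at 10% and about 4 to 8 points at 20%. These figures rest on an assumed range of centre shares, an assumed skewed distribution of stay, 10 to 14 centres and about 131 analysed patients per arm. Bias and inflated type I error are not at issue, so a significant result from the planned tests would stand. The risk is that a real gain is missed.

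For complications the fault is an unnamed stratum. For satisfaction and mobility it is an unresolved choice of method. The co-primary analyses are outside this point.

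**What to change.** Amend Appendix A and the matching text sections before the analysis:

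- **Stay, drain, catheter, analgesic and opioid totals:** use the centre-stratified Wilcoxon (van Elteren) test, or a linear model with centre where a t-test is meant.
- **Secondary mixed models (pain and QoR-15):** add centre as a fixed effect.
- **Complications:** name centre as the stratum of the Mantel-Haenszel test.
- **Satisfaction and mobility:** reconcile Appendix A with the caption of Figure 4, then include centre in the method kept.
- **Small centres:** fix a rule for pooling very small centres in advance, since a centre with patients in only one of the compared arms adds nothing to a stratified test.

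The choice should not depend on the centre variance observed in the data. Centre is already recorded, so no extra data or patients are needed. The cost is SAP wording, slightly more programming, and about 1 point of power if centre has practically no effect (80.8 vs 79.8% in simulation A).
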